STATISTICAL REPORTING:	Performance will be evaluated for pain, function, quality of life, and planned component position vs post-op component position. Data will be summarized descriptively additional to evaluation of data on surgical technique and instrumentation. Categorical data (e.g., gender or race) will be summarized using counts and percentages with 95% Confidence Interval (CI) limit over the time period of interest. Continuous data, such as age, will be summarized by using means, medians, SD, minimum, maximum, and 95% CI over the time period of interest. Implant survival and return to function will be summarized using a Kaplan-Meier method and presented with rates (as percentages) and CI. Routine summaries of complication data is represented by frequencies and percentages. Sample size is based on a longitudinal data collection model and using functional outcomes as the primary endpoint of interest.

This protocol is written based on guidelines from ISO 14155 : 2011Standard for Clinical Investigation of Medical Devices For Human Subjects – Good Clinical Practice ⁽ⁱ⁾ the ICH Guideline on Good Clinical Practice⁽ⁱⁱ⁾, and the Declaration of Helsinki ⁽ⁱⁱⁱ⁾ and is in accordance with US Code of Federal Regulations 21 CFR Parts 11, 50 and 56 ^(iv). IRB or EC approval for each site will be obtained prior to conducting this study, as applicable.

III. Data Collection Overview

The following table indicates the necessary case report forms to be completed at the given time point:

Form Name	Pre-op	Operative	6 Week	3 Month	1 Year
Informed Consent	●				
Inclusion/Exclusion Criteria	X				
Demographic Evaluation	X				
Pre-op plan for Conventional Instrumentation		X			
Operative Information		X			
Surgical Device Information		X			
Discharge Summary		X			
Physical Exam			X	X	X
Objective Knee Assessment	X		X	X	X
EQ-5D	●		●	●	●
Oxford Knee Score	●		●	●	●
Physician Assessment of Radiographs	X*		X	X*	X
Adverse Event Report		★	★	★	★
Protocol Deviations	★	★	★	★	★
Study Completion	★	★	★	★	★

* Long Leg Radiograph required at this interval

* Central or Independent radiographic review performed by Sponsor's designee, if applicable, at discretion of the Sponsor

The following table indicates the necessary case report forms required to be completed for revision patients:

Form Name	Revision (as applicable)	Comments
Physician Assessment of Post-op Radiographs	★	Mark the "pre-revision" exam period.
Adverse Event Report	★	Document adverse event resulting in the revision

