In addition to patient outcomes, the ultimate shortcoming of an arthroplasty is the need for revision. A major factor affecting the rate of knee arthroplasty failure is tibiofemoral alignment. Although there is a vivid discussion with regard to the ideal positioning of implant component, there is still wide consensus that unintentional component malplacement should be avoided, as this can have an adverse impact on implant function and longevity⁷⁻¹⁰. Revision of joint arthroplasty increases load on the health-care system and also incurs significant costs, with a revision total knee arthroplasty estimated to cost a multiple of primary procedures, depending on complexity and indication¹¹. Therefore, there is an economic, as well as clinical, case for maximizing outcomes from primary knee arthroplasties. Further shortcomings of existing strategies are inter-surgeon variability and variation in quality of outcomes. There is a lack of precise reproducibility of surgeon's experience, and most procedures have a relatively steep learning curve.

The primary aim of robotics in arthroplasty is precise reproduction of the surgeon's preoperative plan during surgery. It is hypothesized that more accurate implant placement will translate to better clinical placement, which will translate to better clinical outcomes, although the current data supporting improved patient satisfaction are conflicting. Robotics offers several other potential advantages. The ability to create a preoperative plan and accurately execute it during surgery using intraoperative feedback reduces variation in component placement. This benefit may also be true for less experienced surgeons.

The ROSA Knee System is the natural progression of technology, combining imaging modalities, patient specific guides, navigation, and soft tissue respecting philosophies; all applied to one concise tool which provides reproducible patient outcomes. In addition, it's coupled with precision-engineered industry-leading products: NexGen, Persona, and Vanguard total knee systems. The ROSA Knee system provides streamlined workflow that is customizable to surgeon's needs, and keeps the surgeon in control - bridging the patient satisfaction gap through more precise and accurate cuts, and providing a personalized fit and positioning that can be adapted to the patient intraoperatively.

V. Study Objectives

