A **Delegation of Authority Log** (Appendix C) will be maintained throughout the study and will contain the names, initials, signatures and study responsibilities of all site personnel/designees involved in study procedures and data collection. The **Delegation of Authority Log** will be filed in the site Regulatory Binder for the study.

g. Baseline / Pre-operative Assessment

Baseline/pre-operative data to be collected on the following source documents at the time of enrollment:

1. Inclusion/Exclusion Criteria
2. Demographic Evaluation
3. Pre-op plan for Conventional Instrumentation (when applicable)
4. Physician Assessment of Radiographs (Long-Leg)
5. Objective Knee Assessment

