2. EQ-5D
3. Oxford Knee Score
4. Objective Knee Assessment
5. Physician Assessment of all Follow-up Radiographs
6. Adverse Event Report (as applicable)
7. Protocol Deviations (as applicable)
8. Study Completion (as applicable)

Subjects will be followed post-operatively for 1 year. Unless the study is otherwise closed, data will continue to be collected until the subject completes the study per the protocol, voluntarily withdraws from the study, is withdrawn from the study by the investigator, is lost to follow-up, undergoes revision to remove a study device, or expires. See Management of Incurrent Events (Section IX, Subsection D of this protocol) for additional details. Reason(s) for study completion must be documented on the **Study Completion** case report form.

k. Minimization of Subjects Lost to Follow-up

Subject follow-up is extremely important for the conduct of a clinical study, and the expectation is to maintain the highest possible rate of follow-up compliance throughout this study. During the informed consent process and at each follow-up interval, subjects should be counseled on the importance of completing future study follow-up intervals.

I. Radiographic Definitions and Methods

1. Required radiographic views

Radiographs will be performed at the following intervals:

Clinical Interval	Required Radiograph	Approximate Visit Window
Pre-op	AP and ML long-leg Optional: Skyline view	N/A
6 Week	AP and ML short film or long-leg Optional: Skyline view	7-63 days post-op
3 Month	AP and ML long-leg Optional: Skyline view	-/+1 month
1 year	AP and ML short film or long-leg Optional: Skyline view	-/+2 months

Investigators may obtain additional radiographs within their normal standard of care but the Sponsor will not require notification, unless an Adverse Event is identified.

Preoperative Radiographs:

All preoperative radiographic evaluations performed according to the protocol will be reviewed by the Investigator at the time of the evaluation and documented using the **Physician Assessment of Pre-Op Radiographs** form. Preoperative radiographs will be evaluated using Kellgren-Lawrence Osteoarthritis grading for both medial and lateral knee compartments.

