Anteroposterior (AP) and mediolateral (ML) long-leg radiographs are required for pre-operative planning of the operative knee. Skyline view radiographs are optional. Sites collecting skyline view as part of their standard of care will be asked to submit these radiographs to the Sponsor.

Postoperative Radiographs:

All postoperative radiographic evaluations performed according to the protocol will be reviewed by the Investigator at the time of the evaluation and documented using the **Physician Assessment of Post-Op Radiographs** form. An **Adverse Event Report** form must be completed for those findings identified as an adverse event.

AP and ML long-leg radiographs are required for the 3 month post-operative radiograph of the operative knee. Skyline view radiographs are optional. Sites collecting skyline view as part of their standard of care will be asked to submit these radiographs to the Sponsor.

**The 3 month post-operative film will be used as the baseline radiograph.*

Radiographs should have similar exposure and must show all TKA components and surrounding bone. For consistency, every effort should be made to capture all radiographic views for a given subject using the same institution throughout the study. However, radiographs captured at a different institution may be used for the study, provided they meet required study specifications and are captured within the required interval window. The investigative site will retain copies (hard copy/CD/digital) of all radiographs referenced for the study.

2. **Submission to Sponsor**

At the Sponsor's discretion, study radiographs may be requested from the sites for independent radiographic review and assessment of appropriate parameters.

m. Recommended Revision Procedure

See Management of Incurrent Events (Section IX, Subsection D of this protocol)

X. Reporting

The Sponsor will collect all data in a central database. The management of all study data received by the Sponsor will be the responsibility of the Sponsor or its Designee. The use or

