- Complete header information consistently across all source documents for each individual study subject (when study-specific forms are used).
- Be sure that data on the source documents match that which is entered through the electronic data capture (EDC) system

- Use the study subject's unique Case ID number assigned as instructed. Do not provide information that is not requested on the source document.
- Ensure that all fields are completed. For fields completed by the subject, efforts should be made to obtain any missing responses prior to the subject completing their visit.

Pre-operative planning and final post-operative component positioning data will be extracted from The ROSA Knee System at the discretion of the sponsor. This data will be uploaded by the sponsor into the electronic data capture (EDC) system.

2. Data Submission

Completed source documents will be submitted directly to the Sponsor by electronic data capture and submission via a method approved by the Sponsor. Every effort must be made to ensure data submission to the Sponsor is made within 14 days of the visit completion.

3. Quality Assurance of Data

The Investigator should ensure the accuracy, completeness, legibility, and timeliness of the data reported to the Sponsor in the source documents and in all required reports. Data reported on the source documents and clinic records should be consistent, or the discrepancies should be explained. All electronic systems used to create, modify, maintain, or transmit electronic study records will be validated according to 21 CFR Part 11(ii). The Sponsor will maintain quality control systems, in accordance with the Sponsor's policies and procedures.

C. **Reporting Requirements**

1. Investigator Reporting Responsibilities

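### No baseline limb-alignment measure common to both arms is specified for a non-randomised comparison of component position and radiographic parameters; for the required pre-operative long-leg film the protocol names only Kellgren-Lawrence grading

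*Combined protocol and SAP*

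**What the plan says.** **Films.** Section IX, subsection l (Radiographic Definitions and Methods) requires AP and ML long-leg films pre-operatively and at 3 months. Short films are allowed at 6 weeks and 1 year. The purpose given for the first film is planning: "long-leg radiographs are required for pre-operative planning of the operative knee". The 3-month film, not the pre-operative one, is designated the baseline radiograph.

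**Pre-operative reading.** "All preoperative radiographic evaluations performed according to the protocol will be reviewed by the Investigator at the time of the evaluation" and entered on a pre-operative radiograph form. The only content named for that reading is: "Preoperative radiographs will be evaluated using Kellgren-Lawrence Osteoarthritis grading for both medial and lateral knee compartments".

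**Other baseline sources.** An "Objective Knee Assessment" is completed before surgery and at each follow-up visit (Sections III and IX.g). Conventional cases have their own pre-operative plan form. For robotic cases, Section X.B says: "Pre-operative planning and final post-operative component positioning data will be extracted from The ROSA Knee System at the discretion of the sponsor". Section IX.l adds that, at the sponsor's discretion, "study radiographs may be requested from the sites for independent radiographic review and assessment of appropriate parameters". The parameters are not named.

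**Comparison and analysis.** Section V makes comparison of the two techniques the primary objective. It lists planned versus actual component position, and radiographic parameters as part of clinical performance. No randomisation or other rule for assigning technique is described; Section IX.d asks for consecutive and concurrent enrolment. Section XII is descriptive. It mentions subgroups by indication but no adjustment for baseline differences.

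**The concern.** Because technique is not assigned at random, knees with more deformity may be steered towards one technique. Offering participation to consecutive patients limits selection into the study, not selection of technique within it. The eligibility criteria restrict hip pathology but set no limit on knee deformity, so the arms are free to differ on it.

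The protocol itself treats alignment as important. Section IV counts leg alignment among the determinants of arthroplasty outcome and states: "A major factor affecting the rate of knee arthroplasty failure is tibiofemoral alignment". If pre-operative deformity influences both the choice of technique and the final position, an unadjusted difference between arms mixes the effect of the instrument with the effect of case mix. A confidence interval does not show this. Section XII allows the summaries to support regulatory submissions and publications, so readers may take the difference as an effect of the robot.

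The film from which deformity could be measured is already required in everyone. What is missing is a stated instruction to measure it, in the same way in both arms, and to use it.

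**Working it through.** **1. Is a common baseline alignment measure specified anywhere?**

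| Possible source | Which arm | What the protocol says of its content |
|---|---|---|
| Pre-operative radiograph form (IX.l) | both | Kellgren-Lawrence grade by compartment; other fields not shown |
| Objective Knee Assessment (III, IX.g) | both | items not listed; nothing says it uses the film |
| Pre-operative plan form (III, IX.g) | conventional only | fields not shown |
| Planning data from the robot (X.B) | robotic only | extracted at the sponsor's discretion; content not listed |
| Independent review of films (VI, IX.l) | both, if requested | optional; parameters not named |

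No row names an alignment angle or a varus/valgus class. The two rows most likely to hold one differ by arm in source and in certainty of collection. Even if both contain alignment, the same measurement by the same method is not assured.

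**2. Is any use of such a measure specified?** No. Section XII gives counts, percentages, means, medians, SDs, 95% CIs and Kaplan-Meier rates. Subgroups by indication do not stand in for deformity.

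**3. Plan's own figure.** The arm ceilings in Section VI are 180 robotic and 120 conventional: 180 + 120 = 300, which matches the stated maximum. This is a cap. The plan has no power calculation and gives no SD.

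**4. Illustration in degrees.** The 180 and 120 are the plan's ceilings; every other input is an assumption.

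- Random error: sqrt(1/180 + 1/120) = 0.1179. The 95% CI half-width for a difference in means is 1.96 × 0.1179 × SD = 0.231 × SD. With an assumed SD of 2.5 degrees it is 0.58 degree.
- Bias = (difference between arms in mean baseline deformity) × (degrees carried into the result per degree of deformity). With 2 to 4 degrees and 0.1 to 0.2:

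| Imbalance | Carry-over 0.1 | Carry-over 0.2 |
|---|---|---|
| 2 degrees | 0.2 | 0.4 |
| 4 degrees | 0.4 | 0.8 |

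- Crossing point: at carry-over 0.2 the bias equals 0.58 when the imbalance is 0.58 / 0.2 = 2.9 degrees. At an imbalance of 4 degrees it does so when carry-over is 0.58 / 4 = 0.145. At carry-over 0.1 it never does within this range (maximum 0.4).
- Dependence on SD: the largest bias, 0.8, exceeds the half-width only if the SD is below 0.8 / 0.231 = 3.5 degrees. The smallest, 0.2, does so only if the SD is below 0.2 / 0.231 = 0.87 degree.

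**5. Illustration free of units.** If baseline deformity differs by 0.1 to 0.5 SD between arms and correlates 0.2 to 0.5 with the outcome, the bias is 0.1 × 0.2 = 0.02 SD to 0.5 × 0.5 = 0.25 SD, against a half-width of 0.231 SD. If the techniques truly did not differ, a nominal 95% interval for the difference would exclude zero in 5.3% of studies at the low end and about 56% at the high end. Neither set of assumptions comes from the documents.

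**The case against.** **A reader might infer that baseline deformity is not recorded at all.** The documents do not show that. Section IX.l does not say that the grade is the sole reading, the same film is used for planning, and the fields of the radiograph form, the knee assessment, the conventional plan form and the robot data are not in the documents. What stands is narrower: no measure is named, and none is assured to be common to both arms.

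**A reader might infer that the confounding could never be addressed later.** That is also unsupported. Sites retain copies of all study radiographs, the sponsor may call for independent review, and Section VI permits one central reader for all films. The angle can be read retrospectively. But that review is optional, and a reading method chosen after results are known is weaker than one stated beforehand.

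**Limb alignment is not a named outcome.** This is correct. The objectives name planned versus actual component position and unspecified radiographic parameters. Deviation from a patient's own plan need not behave like residual malalignment, so the calculation in degrees may not carry over to it. Nor do the documents say that deformity drives the choice of technique; that is plausible but assumed.

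**The study is descriptive, and deformity is one confounder among several.** Both are true. A descriptive analysis with a comparative primary objective still yields a difference that will be interpreted. Adjusting for one angle does not make up for the missing rule on how technique is chosen, and this point does not claim that it does.

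**Conclusion.** The point holds as a gap in specification, not as proof of missing data. For the required pre-operative long-leg film, the protocol names only an osteoarthritis grade. It specifies no baseline limb-alignment measure common to both arms and no use of one, although it compares component position and radiographic parameters between non-randomised groups.

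The size is unknown from the documents. Under the stated assumptions the bias runs from about a third of the 95% CI half-width (0.2 against 0.58 degree) to somewhat more than it (0.8 against 0.58). It exceeds the half-width only when imbalance and carry-over are both towards the top of their ranges. This rests on an assumed SD of 2.5 degrees, on full enrolment to both ceilings, and on deformity affecting both choice of technique and result. The case for the change is its low cost and a plausible risk, not a demonstrated bias.

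**What to change.** - **Section IX.l:** add the coronal hip-knee-ankle angle to the investigator's reading of the pre-operative and 3-month AP long-leg films, with the same method and the same form in both arms.
- **Section XII:** tabulate the pre-operative angle by technique. Present the between-technique position and radiographic comparisons adjusted for it or stratified by it, alongside the unadjusted summaries. State that this addresses deformity only and that other confounding remains.

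**Cost.** No extra imaging and no extra staff: the films are already required and already read by the investigator. Allow about a minute per film (an estimate), one form field if it does not already exist, back-reading of retained films for subjects already enrolled, and a little more analysis. If the form already carries the angle for both arms, the change reduces to stating so in IX.l and adding the analysis to XII.

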6. EQ-5D
7. Oxford Knee Score
8. Protocol Deviations (as applicable)
9. Study Completion (as applicable)

h. Surgical Technique

Through the use of either conventional or robotic techniques, standard operating procedures will be followed and all surgical procedures will be performed under aseptic conditions.

Investigators will implant all commercially available Persona, NexGen, and Vanguard Total Knee components in compliance with corresponding labeling requirements, and in accordance with appropriate surgical technique(s).

i. Surgical and Immediate Post-Surgical Procedures (Data Collection)

Surgical and immediate post-surgical data to be collected on the following source documents:

1. Operative Workflow
2. Surgical & Operative Information
3. Discharge Summary
4. Adverse Event Report (as applicable)
5. Protocol Deviations (as applicable)
6. Study Completion (as applicable)

Post-surgical management for study subjects will follow the investigator's standard of care for patients undergoing total knee arthroplasty (e.g. prophylactic antibiotic therapy, prevention of deep vein thrombosis, prevention of pulmonary embolism, etc.). Post-surgical rehabilitative therapy will be as prescribed by the investigator.

j. Post-operative Follow-up procedures (Data Collection)

Post-operative clinical evaluations/assessments will be conducted at the following visit intervals:

Clinical Interval	Interval Window in Days Post-op*	Approximate Window in Weeks or Months Post-op*
6 weeks	21 to 63 days	-/+3 weeks
3 months	61 to 120 days	-/+1 month
1 year	300 to 420 days	-/+2 months

*Visit(s) outside of window will be determined based on Days Post-op

Post-operative clinical data will be collected on the following case report forms:

1. Physical Exam

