**Study completion is only required for subjects with femoral or tibial component revisions. Subjects with articular surface revisions will remain in the study.*

4. Investigator Withdrawal

The Investigator can choose to withdraw a subject from the study if the subject no longer meets study inclusion/exclusion criteria. The reason for the Investigator’s withdrawal of the subject must be documented on the **Study Completion** form.

5. Subject Withdrawal

Study subjects may choose to withdraw from the study at any time, for any reason. If possible, a final evaluation will be completed for any subject who no longer wishes to participate in the study. The reason for the subject withdrawal must be documented on the **Study Completion** form.

6. Lost to Follow-up

Subject follow-up is extremely important for the conduct of a clinical study, and the expectation is to maintain the highest possible rate of follow-up compliance throughout this study. During the informed consent process and at each follow-up interval, subjects should be counseled on the importance of completing future study follow-up intervals. In an effort to minimize lost-to-follow-up subjects, the following recommendations and/or study requirements are essential to ensure proper patient selection and compliance:

1. Patient Eligibility: Subjects will be selected according to the study inclusion/exclusion criteria and are expected to return for all follow-up visits.
2. Patients Counseled: Patients will be counseled during the informed consent process on the importance of returning for follow-up visits.
3. Patient Exclusion: Patients who are not willing to return for study required follow-up visits and/or are not willing to comply with the follow-up schedule will not be considered for enrollment into the study.
4. Contact Tracking: Attempts to contact subjects will be documented in the study subject’s medical record.

A study subject will be considered lost to follow-up after they have missed a visit and attempts to locate and evaluate the subject using the procedure outlined below have failed. All attempts to contact the subject are to be documented in the subject’s medical record and on the **Study Completion** form. Missed visit(s) also must be documented using the **Protocol Deviations** form, unless the visit is retrospective. The first three contact attempts should be made by telephone, with additional attempts as outlined in the following table:

If	Then

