a response is not received after three (3) phone calls,	the Investigator or Designee should send a letter to the subject explaining the follow-up agreement per the Informed Consent, and requesting a response from the subject.
all attempts to contact the subject are unsuccessful or the subject is contacted and chooses to withdraw from the study,	a Study Completion form will be completed and will specify the reason the subject is no longer participating in this study.

7. Protocol Deviations

Investigators should not deviate from the study protocol, unless patient safety is at risk. If a protocol deviation does occur, the deviation must be documented on the **Protocol Deviation** form and submitted to the Sponsor. If applicable per their reporting requirements, the Investigator or Designee will also report applicable protocol deviations to their IRB or EC.

8. Study Termination

Study subject participation is expected to end upon completion of the subject's last follow-up visit unless the subject voluntarily withdraws from the study, is withdrawn from the study by the Investigator, is lost to follow-up, undergoes revision to remove a study device, or expires. Reason(s) for study completion must be documented on the **Study Completion** form.

If the Sponsor decides to terminate the study early, the Sponsor will inform the Investigators of the reason for early study termination. It is the responsibility of the Investigators to inform their IRB or EC as applicable according to local and national laws/regulations.

9. Modification of the Protocol/Clinical Investigation Plan

All amendments to this clinical protocol shall be agreed to by the Sponsor and be recorded with a justification for the amendment prior to implementation. Approval of the applicable IRB or EC must be obtained prior to implementation, if required according to the local and/or national laws/regulations.

E. Medical Events/Adverse Events Definitions and Classifications

An adverse event is any unfavorable or unintended sign, symptom, or disease that impacts the operative knee, such as musculoskeletal. Adverse event is synonymous with complication or medical event.

1. Classification of the Event

Adverse Event (AE)⁽ⁱ⁾:

An Adverse Event is defined as any untoward medical occurrence, unintended disease or injury, or untoward clinical signs (including abnormal laboratory findings) in subjects, users or other persons, whether or not related to the investigational medical device.

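### Section X.D.6 closes out a subject who misses an early visit and cannot be reached, with no further contact attempt required for the 1-year visit

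*Combined protocol and SAP*

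**What the plan says.** Section X.D.6 (Lost to Follow-up) defines the status: "A study subject will be considered lost to follow-up after they have missed a visit and attempts to locate and evaluate the subject" by the set procedure have failed. The procedure starts with the telephone: "The first three contact attempts should be made by telephone, with additional attempts as outlined in the following table". If three calls go unanswered, "the Investigator or Designee should send a letter to the subject explaining the follow-up agreement per the Informed Consent". If everything fails, "a Study Completion form will be completed and will specify the reason the subject is no longer participating in this study". The same section has missed visits recorded on the Protocol Deviations form. It gives no spacing or deadline for the calls and letter, and it treats the 6-week, 3-month and 1-year visits alike.

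Two other sections give the status its effect. Section IX.j states "Subjects will be followed post-operatively for 1 year" and that "data will continue to be collected until the subject completes the study per the protocol, voluntarily withdraws from the study", and the sentence goes on to name loss to follow-up among the endings. Section X.D.8 (Study Termination) says "Study subject participation is expected to end upon completion of the subject's last follow-up visit unless the subject voluntarily withdraws from the study", and again loss to follow-up is among the exceptions.

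The 1-year visit window in Section IX.j is "300 to 420 days" after surgery. No section asks for a new contact attempt in that window after an earlier close-out, or describes how a closed subject could re-enter.

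**The concern.** The trigger is a single missed visit of any kind, once tracing has failed. Applied at 6 weeks or 3 months, it ends follow-up while the whole 1-year window still lies ahead. Failing to answer calls and a letter in the first months does not show that the subject would be out of reach at 1 year.

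Three features of this study make that worth attention.

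- The 1-year visit is the last and longest point for the Oxford Knee Score and EQ-5D. Sections II and XII.A also plan Kaplan-Meier summaries of implant survival, where early closure means early censoring.
- The stated objective is a comparison of robotic and conventional instrumentation, and no random allocation is described. Loss that differed by group and was related to outcome would add to whatever imbalance already exists.
- Section XII is descriptive and names no method for missing data, so retaining subjects is the main safeguard available.

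**Working it through.** There is no plan figure to reproduce. Section XII.B states that there are no hypotheses, and the documents give no power, effect size or dropout allowance. The check is a reading of the rule, date arithmetic, and an illustration on assumed rates.

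**1. Does the status stop data collection?** Yes. X.D.6 assigns it and files the completion form; IX.j and X.D.8 each list it as an ending. It is more than a label.

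**2. When can it apply?** Windows from the table in Section IX.j, in days after surgery:

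| Visit | Opens | Closes |
|---|---|---|
| 6 weeks | 21 | 63 |
| 3 months | 61 | 120 |
| 1 year | 300 | 420 |

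- Close of 6-week window to opening of 1-year window: 300 − 63 = 237 days; to its close: 420 − 63 = 357 days.
- Close of 3-month window to opening of 1-year window: 300 − 120 = 180 days; to its close: 420 − 120 = 300 days.
- After a missed 6-week visit, up to 120 − 63 = 57 days of the 3-month window also remain. Section IX.l makes the 3-month film the radiographic baseline, and it is the only postoperative interval at which long-leg views are mandatory.

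The gaps run from the close of the missed window. Actual close-out comes later by however long the calls and letter take, which the protocol does not state.

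**3. How many assessments?** Both rates below are assumptions, and 300 is the enrolment ceiling (180 + 120).

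- Unreachable after an early visit, 5% to 10%: 300 × 0.05 = 15; 300 × 0.10 = 30.
- Of these, a third to a half could be seen at 1 year: 15 × 1/3 = 5; 30 × 1/2 = 15.
- Forgone: 5 to 15 assessments, or 5/300 = 1.7% to 15/300 = 5%.
- With wider assumptions of 2% to 10% and 25% to 75%: 300 × 0.02 × 0.25 = 1.5 to 300 × 0.10 × 0.75 = 22.5.

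**4. Precision.** The 95% half-width for a difference in means, in SD units, is 1.96 × √(1/n₁ + 1/n₂). Let a share d be closed and a share r of those be recoverable, the same in both arms.

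- d = 5%, closed out: n = 171 and 114, half-width 0.237.
- d = 5%, r = 50%, recovered: n = 175.5 and 117, half-width 0.234. Closing out widens the interval by 1.3%.
- Over the wider ranges in step 3, the widening is about 0.3% to 4.1%.

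**5. Selective loss.** If the recoverable subjects in one arm differ in mean outcome from those observed by Δ, leaving them out moves that arm's mean by Δ × dr / (1 − d(1 − r)).

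- d = 5%, r = 1/3: 0.0167/0.9667 = 1.7% of Δ.
- d = 10%, r = 1/2: 0.05/0.95 = 5.3% of Δ.

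The documents do not give Δ. For rare events a single case counts for more: one unrecorded revision in a conventional arm of 120 is 1/120 = 0.83 percentage points of the crude proportion.

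**The case against.** The strongest reply is that the rule is narrower than it first appears, and much of this stands.

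- A reader might infer that anyone who skips one visit is dropped. The text does not say so. Close-out needs a missed visit and the failure of three calls and a letter. A subject who can be reached stays active unless he or she withdraws, and the missed visit is recorded as a deviation.
- A reader might infer that data are thrown away. Nothing already collected is removed; only later data are not sought.
- A reader might infer that a closed subject's later revision can never be recorded. That is not settled. Section X.D.2 has adverse events documented for the whole of the investigation, and Section III provides revision forms, while IX.j ends data collection at loss to follow-up. The passages leave an ambiguity rather than a bar.
- A reader might infer a contradiction with the section's aim of the highest possible follow-up. The aim is paired with counselling, patient selection and a tracing procedure, so the rule falls short of the aim without contradicting it.
- With no deadline for the attempts, a site could hold a subject open longer. This is true, but nothing requires it, and practice could differ among up to 10 sites.
- Some unreachable subjects would never return, and one who missed 3 months would lack the baseline film, so part of the 1-year radiographic comparison would stay incomplete. The questionnaires and implant status would still be usable.

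None of this supplies a required attempt at the 1-year visit for a subject already closed out.

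**Conclusion.** The point holds in a limited form. As written, X.D.6 with IX.j and X.D.8 ends follow-up for a subject unreachable after the 6-week or 3-month visit, with the full 1-year window still to come and no required re-contact. Obtainable 1-year Oxford Knee Score, EQ-5D and implant-survival follow-up is forgone.

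The size is not known. The figure of 5 to 15 assessments rests wholly on two assumed rates and on enrolment reaching 300; other plausible rates give 1.5 to 22.5. The cost in precision is small, and no power or sample-size statement is affected because none exists. The main concern is selective missingness. The documents give no evidence that those who become unreachable differ by outcome or by arm, so this is a risk and not a shown bias. The change is worth making because it is cheap.

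**What to change.** Amend Section X.D.6, including the row of its table that sends unsuccessful contact straight to a Study Completion form:

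- Keep the three calls and the letter after every missed visit, and keep recording the missed visit as a protocol deviation.
- If a 6-week or 3-month visit is missed and contact fails, keep the subject active and repeat the contact attempts for each remaining visit.
- Complete the Study Completion form as lost to follow-up only when the 1-year window closes at day 420 without contact.
- Split the table row, so that a subject who is contacted and chooses to withdraw is still closed at that time. Withdrawal, death, revision and the other listed endings are unchanged.

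Sections IX.j and X.D.8 can stand, since they rely on the X.D.6 definition. The cost is a few more contact attempts per affected subject, records that stay open longer, and a minor amendment. Under Section X.D.9 that amendment needs sponsor agreement, a recorded justification and, where required, IRB or EC approval at up to 10 sites.
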